## Introduction

Anatomical limitations to implant insertion in fully edentulous arches are frequently encountered in the posterior regions of the jaws, due to the presence of the mandibular canal and of the maxillary sinus. In such situations, the installation of standard implants ( $\geq 10$  mm) could be impossible.

An alternative might be the use of the so-called “tilted implants” that might allow the use of standard implants. Vertical augmentation procedures or sinus floor elevation might allow the installation of standard implants as well. Another alternative is the use of short implants, as recommended in a consensus conference for the lower occurrence of complications of this treatment compared the use of longer dental implants installed in augmented sinus. Another consensus report concluded that the use of  $\leq 6$  mm long implants are a valid option to be used as alternative to augmentation procedures to reduce morbidity incidence.

A recent article reported a high survival rate (91.7%) after 10 years of loading of 6 mm long implants supporting single FDPs in the posterior regions of both jaws. Recently, 4 mm long implants with a standard diameter have been used for the restoration of the posterior edentulous mandible with favorable results. However, RCTs reporting the results from full-arch FDPs that included 4 mm long implants placed in the posterior regions of the maxilla have not been published yet.

Hence, the aim of the present study will be to compare the survival and success rates of 4 mm implants used as distal support of a maxillary full-arch FDPs with standard (10 mm) implants placed in association with a bilateral sinus floor augmentation procedure.

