### *Study population*

This study will be designed as an RCT study. Twenty patients have been planned to be included in the present RCT. Two parallel groups will be randomly arranged, the Short group that will include the 4 mm long implants, and Standard group that will include only 10 mm long implants installed 4 months after bilateral sinus floor elevation. Participants recruitment and all clinical procedures will be performed at the Department of Biomedical and Neuromotor Sciences, Dental Clinic, University of Bologna, RN, Italy.

The following inclusion criteria will be adopted:

- Edentulous maxilla
- Willing to receive a full arch fixed restoration in the maxilla.
- Latest extraction at least 8 weeks before implant insertion
- Sinus floor height included between 4 to 6 mm
- Bone width in the distal segments sufficient to allow the insertion of a 4 mm long implant of standard diameter.
- In the anterior maxilla (from first premolar to first premolar) bone width sufficient to allow the insertion of 10 mm long implants of standard diameter.

Minor horizontal augmentations with GBR procedures was allowed in the anterior maxilla.

Moreover, the opposing arch have to present one of the following conditions:

- natural dentition (at least 10 elements from 3.5 to 4.5)
- FPDs of at least 10 elements (from 3.5 to 4.5) supported by teeth or implants
- Implant supported or teeth supported overdentures
- Adequate partial removable prostheses.

*Exclusion criteria:*

Systemic exclusion criteria

- Presence of conditions requiring prophylactic use of antibiotics (e.g., history of rheumatic heart disease, bacterial endocarditis, cardiac valvular anomalies, prosthetic joint replacements).

- Major systemic diseases, or medical conditions requiring prolonged use of steroids, or alcoholism or chronically drug abuse.
- Current pregnancy or breastfeeding women
- Smokers > 10 cigarettes per day
- Physical handicaps that would interfere with the ability to perform adequate oral hygiene
- Immunocompromised patients including patients infected with HIV
- Conditions or circumstances, in the opinion of the investigator, which would prevent completion of study participation or interfere with analysis of study results, such as history of non-compliance, or unreliability.
- Patients with an ongoing or previous treatment with bisphosphonates (for at least 2 months for oral therapy or 6 months for IV injection)

*Local exclusion criteria*

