- Local inflammation, including untreated periodontitis
- Pre-cancerous oral lesions
- History of local irradiation therapy
- Severe bruxism or clenching habits
- Patients with inadequate oral hygiene or unmotivated for adequate oral home care
- Previous GBR or GTR treatment at the implant site
- Total removable prosthesis in the lower arch

*Randomization and assignment concealment*

A statistician not involved in the study performed the randomization in blocks of four and the assignments will be sealed in coded and opaque envelopes.

*Masking Procedure:* The surgeon will be blinded about the assignment until the time of the surgery. The outcome assessor will be blinded about the protocol.

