#### *Surgical procedures in the Short group*

In each side of the posterior region of the maxilla, one tissue level implant, 4 mm long and 4.1 mm in diameter, will be installed. In the frontal region, four bone level implants, 10 mm long and 4.1 mm or 3.3 mm in diameter will be installed

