### *Data analysis*

Mean values will be obtained from the double measurements made at the mesial and distal aspects of each implant. Mean values will be calculated between the distal and mesial measurements for each implant.

At the tissue level implants, the height of the polished neck (1.8 mm) will be subtracted to obtain the level of the coronal margin of the rough surface. The marginal bone levels reported in the present article will be related to the position of the coronal marginal rough surface. Marginal bone changes over time will be calculated and differences between groups will be evaluated at implant level using

the Mann-Whitney test included in the Statistics software SPSS (IBM Inc., Chicago, IL, USA) The level of significance will be set at  $\alpha=0.05$ .

The primary variable will be the change of marginal bone level between the baseline and 1 and 2 years of follow-up.

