### *Outcomes*

#### PRIMARY OUTCOMES

TITLE: Survival rate of 4 mm implants

DESCRIPTION:

-To compare the survival rate of 4 mm implants used as distal support of a maxillary full-arch FDPs with standard (10 mm) implants placed in association with a bilateral sinus floor augmentation procedure.

TIME FRAME: 24 months

TITLE: Changes of crestal bone level

DESCRIPTION: Change of crestal bone level measured on intraoral x-ray applying a parallel technique from baseline (definitive prosthesis delivering) and 2-year follow-up. The distance between the implant margin and the first bone to implant contact will be measured in millimeters at the mesial and distal aspects of the Short and Standard implants.

TIME FRAME: 24 months

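### The plan yields a p-value for bone change and nothing for survival; both primary outcomes need a patient-level estimate with a 95% confidence interval

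*Combined protocol and SAP*

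**What the plan says.** The Data analysis section averages repeated readings and the mesial and distal sites to one value per implant and computes change over time. It then states that "differences between groups will be evaluated at implant level using" "the Mann-Whitney test included in the Statistics software SPSS", with the significance level set at 0.05. No other inferential method appears anywhere. The section does not say whether the test is two-sided, and it names no effect estimate or confidence interval. Its primary variable is bone change from baseline to 1 and 2 years.

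The Outcomes section lists two primary outcomes, both at 24 months. The first is survival: "To compare the survival rate of 4 mm implants used as distal support of a maxillary full-arch FDPs" with that of the 10 mm implants placed after sinus augmentation. The second is change in crestal bone level. No test, estimate or interval is given for survival.

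On size, the Study population section says only "Twenty patients have been planned to be included in the present RCT", with no power, effect size, SD or margin.

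**The concern.** The stated aim is comparative. A Mann-Whitney p-value gives no difference in millimetres and no range of differences compatible with the data. For survival the plan gives not even a p-value. With 20 patients both comparisons will be imprecise, and the plan provides no way of showing how imprecise.

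Two consequences follow. If p exceeds 0.05, readers have nothing to stop them taking the two strategies as equal. And because estimate, unit and main time point are not fixed in advance, whoever adds an interval at the reporting stage can choose between implant and patient and between 1 and 2 years after seeing the data. An interval that treated the implants as independent would also be too narrow.

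**Working it through.** **Inputs from the document**
- Total size: 20 patients (Study population).
- Design: "Two parallel groups will be randomly arranged"; a statistician "performed the randomization in blocks of four". The allocation ratio is not stated. Assuming 1:1, 20 / 4 = 5 blocks with 2 patients per arm in each, so 10 per arm.
- Study implants: "In each side of the posterior region of the maxilla, one tissue level implant" in the Short group, and one implant in each augmented sinus in the Standard group. That is 2 per patient and 10 × 2 = 20 per arm.

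**Assumptions not in the document:** a two-sided 5% level; SD of the patient-mean bone change 0.5 to 1.0 mm; within-patient correlation (ICC) 0.3 to 0.7; normal data in the simulations.

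The figure of 20 patients cannot be reproduced, because no inputs for it are given. The check therefore starts from the fixed size.

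**1. Precision for bone change, patient as unit**
- Half-width = t(0.975, 18) × √(2/10) × SD = 2.101 × 0.447 × SD = 0.94 SD.
- SD 0.5 mm: 0.94 × 0.5 = 0.47 mm. SD 1.0 mm: 0.94 mm.
- This is the t-based width. The Hodges-Lehmann interval is slightly wider, about 0.99 SD on average in simulation.

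**2. Why the implant cannot be the unit**
- With two implants per patient the design effect is 1 + ICC, so 20 implants per arm carry the information of 20 / (1 + ICC): 15.4, 13.3 and 11.8 at ICC 0.3, 0.5 and 0.7.
- I simulated the planned test (20 v 20 implants in 10 v 10 patients, no true difference). The type I error is about 0.09, 0.11 and 0.14 at those ICCs, against the nominal 0.05.

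**3. Precision for survival**
- Wilson upper limit for zero failures in n: z² / (n + z²), with z² = 3.84.
- By patient, n = 10: 3.84 / 13.84 = 27.8%. With zero failures in both arms the Newcombe interval for the difference is therefore about −28 to +28 points. The exact upper limit for a single arm is 1 − 0.025^(1/10) = 30.8%.
- If all 20 implants per arm were independent, the most favourable case: 3.84 / 23.84 = 16.1%, so about ±16 points.
- For scale only, since no survival test is planned: Fisher's exact test on 10 v 10 patients gives p = 0.087 for 4 v 0 patients with a failure and p = 0.033 for 5 v 0.

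**The case against.** **The planned test is not weak against large bone-level differences.** This stands. A reader might infer that, followed as written, the trial will probably give p > 0.05 even when the true difference is large. For bone change the document does not support that. The test runs on 20 v 20 implants, and in simulation over ICC 0 to 0.7 it reaches p < 0.05 in about 63–67% of trials at a true difference of 0.8 implant-level SD and in about 80–85% at 1.0 SD. Part of that apparent strength at positive ICC comes from the inflated type I error, so the risk as written includes false positives as well as missed differences.

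**No equivalence or non-inferiority aim is stated.** This also stands. A reader might infer from the Introduction that the trial must decide whether 4 mm implants are acceptable. The remark there, that short implants are a "valid option to be used as alternative to augmentation procedures to reduce morbidity incidence", reports another group's consensus on implants of 6 mm or less. The trial's own aim is to compare. Nor does the plan say that it will read p > 0.05 as equivalence. An interval without a margin cannot settle acceptability, and none is claimed to here.

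**Authors would report intervals anyway.** The document commits to the CONSORT checklist, but it fixes neither estimate, unit nor main time point for an interval.

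**The remedy changes the plan.** It does: the unit becomes the patient and 24 months becomes the main time point. Both changes should be declared. The first follows from the two implants per patient; the second matches the Outcomes section.

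**Conclusion.** The point holds as a gap in the analysis, and it should be corrected. For bone change the plan gives a p-value computed on the wrong unit; for survival it gives nothing. The precision attainable is about ±0.94 SD for bone change and, with no failures, about ±28 points for survival by patient. A non-significant result is compatible with differences of that order in either direction and would not show that the strategies perform equally.

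The SD multiple and the survival figure rest on 1:1 allocation and complete follow-up. The millimetre range also rests on the assumed SD, and the type I error on the assumed ICC and normal data. The absence of an estimate, an interval and a survival analysis rests on no assumption.

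**What to change.** After the sentence that sets the significance level in the Data analysis section, add:

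> The main result is the Hodges-Lehmann difference (Short minus Standard) in bone change from baseline to 24 months, averaged over each patient's two distal implants, with its 95% CI. The 1-year change is reported in the same way as supportive. Implant survival at 24 months is reported by group, together with the difference in the proportion of patients losing at least one distal implant and its 95% (Newcombe) CI. A p-value above 0.05 will not be reported as equivalence.

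State openly that this moves the unit of analysis from implant to patient and makes 24 months the main time point. The team should also say how a patient with only one remaining distal implant enters the average. No margin is added.

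The cost is a few lines of text and standard output, with no new patients, visits or data. The downside is that the wide intervals will make the conclusion look less favourable.

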## **Abstract**

**Aim:** to compare the survival and success rates of 4 mm implants used as distal support of a maxillary full-arch FDPs with standard (10 mm) implants placed in association with a bilateral sinus floor augmentation procedure.

**Material and Methods:** Two groups will be randomly prepared, the Short group and the Standard group. In the Short group, one 4 mm long and 4.1 mm in diameter implant (extra-short implant) will be installed in each side of the posterior region of the maxilla. In the Standard group, bilateral sinus floor elevations will be performed. After 4 months of healing, one 10 mm long and 4.1 mm in diameter implant (standard implant) will be installed into each augmented sinus. In the frontal region, four 10 mm long implants will be installed in both groups. Clinical assessments and x-rays will be taken at prosthesis delivering (6-8 weeks after implant installation), and after 6, 12, 18 and 24 months.

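### The Data analysis and Outcomes sections disagree on what is primary beyond 24-month bone change, and nothing says which result decides the trial

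*Combined protocol and SAP*

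**What the plan says.** Four places in the combined protocol and SAP bear on the primary outcome.

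- **Data analysis:** "The primary variable will be the change of marginal bone level between the baseline and 1 and 2 years of follow-up". This is one variable at two time points, without survival. The only test named is for bone change: "differences between groups will be evaluated at implant level using" "the Mann-Whitney test included in the Statistics software SPSS", at a single significance level of 0.05.
- **Outcomes, Primary outcomes:** the first entry is "TITLE: Survival rate of 4 mm implants". The second is crestal bone change, measured "from baseline (definitive prosthesis delivering) and 2-year follow-up". Both have a 24-month time frame, and 1 year does not appear.
- **Abstract:** the aim is "to compare the survival and success rates of 4 mm implants used as distal support of a maxillary full-arch FDPs", against standard implants in augmented sinuses.
- **Introduction:** the aim is repeated: "the aim of the present study will be to compare the survival and success rates of 4 mm implants". Neither statement of the aim names bone level.

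The sample size is given under Study population: "Twenty patients have been planned to be included in the present RCT". No effect size, SD, event rate or power accompanies it.

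**The concern.** A confirmatory trial needs one result, or a stated rule over several, that settles its primary conclusion before outcome data are compared. Here a reader following Data analysis would judge the trial on bone change at two times. A reader following Outcomes would judge it on survival and 24-month bone change. A reader following the aim would look to survival and success. These can give different answers, and the plan does not say what is then concluded.

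Two things are at stake. The deciding result could be settled after the data are known. And if any one significant result were accepted as the primary finding, the error rate would exceed the nominal 0.05.

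**Working it through.** **Step 1: set the sections side by side.**

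| Candidate | Data analysis | Outcomes | Aim |
|---|---|---|---|
| Survival, 24 months | not named | primary | named, no time point |
| Bone change, 1 year | primary | not named | not named |
| Bone change, 2 years | primary | primary | not named |
| Success rate | not named | not named | named, not defined |

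Marginal and crestal bone level appear to be the same radiographic measurement (Radiographic measurements section), so the difference in wording is not counted as a conflict. Only 2-year bone change is primary in both sections. No section supplies a hierarchy, an alpha split or an all-must-succeed rule.

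**Step 2: illustrate the size.** The plan gives no figure to reproduce. The inputs are:

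- from the documents: 20 patients, two arms, Mann-Whitney test, alpha 0.05;
- assumed: 10 patients per arm (the ratio is not stated), two-sided tests, normally distributed changes, 1-year/2-year correlation r from 0.5 to 0.85.

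One value per patient is used so that clustering of implants does not enter. There were 200,000 simulated trials per cell.

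*Either bone time point counts, no true difference:*

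| Version of the test | One test | Either of two |
|---|---|---|
| Exact | 4.3% | about 7% (r = 0.85) to 8% (r = 0.5) |
| Asymptotic | 5.2% | about 8% (r = 0.85) to 10% (r = 0.5) |

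At implant level, as the plan writes the test (20 v 20 implants, asymptotic), the figures are 7.6% to 9.0% against 4.9% for one test if a patient's two implants are uncorrelated. They are 15.9% to 19.1% against 10.8% if that correlation is 0.5. The rise in the one-test figure comes from clustering, which is a separate issue.

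*Adding survival.* Patient-level Fisher's exact test has a true size of 0.008% with 5% of patients failing and 0.115% with 10%. Treated as independent of bone change, it adds (1 − 0.0524) × 0.008% ≈ 0.01 points to (1 − 0.0524) × 0.115% ≈ 0.1 points. At patient level the inflation comes almost wholly from the two bone time points.

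*Disagreement between the 1- and 2-year tests, same true difference at both times (asymptotic):*

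| True difference | Tests disagree (r = 0.85 to 0.5) |
|---|---|
| 0.2 SD | 7% to 11% |
| 0.5 SD | 13% to 23% |
| 0.8 SD | 19% to 34% |
| 1.2 SD | 17% to 30% |
| 1.6 SD | 8% to 13% |

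The documents give no effect size, so no row is preferred.

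**Step 3: what survival could show.** With no failing patients in one arm of 10, Fisher's two-sided p is 2 × C(10,k) / C(20,k) for k failing patients in the other arm:

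- k = 4: 2 × 210 / 4,845 = 0.087;
- k = 5: 2 × 252 / 15,504 = 0.033.

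Five failing patients against none are needed. Power is 2.0% for true failure of 20% v 5% of patients, 9.3% for 30% v 5% and 24% for 40% v 5%. Whether survival or bone change leads therefore largely determines what 20 patients can establish.

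**The case against.** The strongest defence is that the conflict is only partial. Two-year bone change is primary in both sections. The Data analysis section deals only with radiographic data, so its primary variable may mean the lead variable of that analysis, with the Outcomes section as the full list. The overlap is real and points to the simplest repair. The milder reading does not remove the problem: the sentence is unqualified, it names two time points without choosing one, and survival is left with no test.

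A second objection is that the error rates assume a significant difference is the hoped-for result. The plan only says the groups are compared and presents short implants as an alternative to augmentation. If similarity is the hope, these rates do not describe the decision. This stands, and the figures are illustrations. The finding rests on the contradiction in the text.

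Three smaller points also stand. A lost implant has no later bone level, so treating survival as independent of bone change is a simplification. Success is undefined, so bone level might have been meant to fall within it. The documents do not show whether outcome data exist: ethics approval dates from 2015, randomization and the PROMs are described in the past tense, and a 2019 paper is cited. A choice made after seeing data is thus a possibility and has not been shown.

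**Conclusion.** The concern holds and should be resolved before analysis. The two sections contradict each other on whether survival and 1-year bone change are primary, the aim matches neither, and no rule says which result decides. This conclusion needs no assumption beyond the text.

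The size is conditional. With 10 patients per arm, one value per patient and r from 0.5 to 0.85, accepting either bone time point raises the false-positive rate to about 7% to 8% (exact) or 8% to 10% (asymptotic). There is no inflation if all outcomes must succeed, but the plan does not say so. Disagreement between the two bone time points would be common at moderate differences, up to about a third of trials at 0.8 SD.

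**What to change.** State the same primary outcome and time point in the Abstract, Introduction, Data analysis and Outcomes sections. Which outcome leads is the sponsor's choice.

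**Option A (simplest).** Make bone change from baseline to 24 months the sole primary outcome at two-sided 0.05. It is already primary in both sections and has a named test. One-year bone change and survival become secondary. Report survival as proportions with 95% confidence intervals, at patient level or allowing for two implants per patient, with no significance claim. The cost is that the sponsor gives up claiming success on those two outcomes, and the aim is reworded.

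**Option B (survival stays primary, as the aim and its first place in the list suggest).** Drop 1 year from the primary variable. Name the survival test and a patient-level unit, for example Fisher's exact test on patients with any failed study implant. State either Holm adjustment or that both outcomes must succeed. The cost is power, with 10 v 10 patients:

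- Under Holm, the bone test must usually pass 0.025. Power falls from about 18% to 11% at 0.5 SD, 39% to 26% at 0.8 SD and 70% to 56% at 1.2 SD.
- If both must succeed, the survival test alone caps power at 2.0% for 20% v 5% failing and 24% for 40% v 5%, so the rule could rarely be met.

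Keeping both bone time points and requiring both gives power of 7% to 12% at 0.5 SD, 22% to 29% at 0.8 SD and 55% to 62% at 1.2 SD, against 18%, 39% and 70% for one test.

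Under either option, record the choice in a dated amendment before outcome data are compared by group, or state what was already known. The same amendment could define or drop success and say how failed implants enter the bone analysis. No new visits or measurements are needed. Whether bone change is tested per implant or per patient is a separate question that this change leaves open.
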